### *Patient Global Impression of Change*

The 7-point PGIC is a subject-reported outcome measure tied to the conceptual framework of overall improvement. It is a recommended and responsive outcome domain for pain-related clinical trials (Dworkin et al. 2005, Farrar et al. 2001).

### *Brief Pain Inventory interference scale*

The BPI interference scale shows reliability and validity for chronic pain and is a core outcome measure for the assessment of the impact of chronic pain on activities of daily living (Dworkin et al. 2005).

### *Pain Disability Index*

The PDI is a brief instrument that was developed to assess pain-related disability, providing information that complements the assessment of physical impairment.

*EuroQol-5 dimension 5 level*

The EQ-5D-5L health questionnaire is a generic health-related quality of life instrument developed by a multidisciplinary team of European researchers. It provides a simple descriptive profile and a single index value that can be used in the clinical and economic evaluation of health care and in population health surveys to assess health outcome from a wide variety of interventions. The EQ-5D-5L is widely used in different countries by clinical researchers in a variety of therapeutic areas.

*Pain Anxiety Symptom Scale*

The 20-item PASS, based on the original 40-item PASS, was developed by McCracken and Dhingra (2002) to assess anxiety related specifically to pain in clinical and research contexts. It shows strong internal consistency, reliability, and good predictive and construct validity.

*Center for Epidemiological Studies Depression Scale*

The CES-D scale was tested in household interview surveys and in psychiatric settings. It was found to have very high internal consistency and adequate test-retest repeatability. Validity was established by patterns of correlations with other self-report measures, by correlations with clinical ratings of depression, and by relationships with other variables which support its construct validity. Reliability, validity, and factor structure were similar across a wide variety of demographic characteristics in the general population samples tested (Radloff 1977).

**Pharmacodynamic assessments***Bone turnover markers*

The bone biomarkers CTX (for resorption) and BAP and PINP (for bone formation) have been selected in accordance with recommendations for the selection of these particular biomarkers in other bone diseases, including osteoporosis (Wheater et al. 2013; Vasikaran et al. 2011). Disordered bone metabolism has been suspected in CRPS based on abnormalities observed on imaging (x-rays, bone densitometry and, in particular, bone scintigraphy using radiolabeled bisphosphonates). The selected markers are known to be responsive to and associated with the mechanism of action of bisphosphonates.

*Bone densitometry and magnetic resonance imaging*

Bone abnormalities, including regional osteoporosis/osteopenia on X-rays and osteolytic lesions identified by uptake of radiolabelled bisphosphonate and triple-phase bone scintigraphy, have been described in patients with CRPS (O'Donoghue et al. 1993; Veldman et al 1993; Wüppenhorst et al. 2010; Ringer et al. 2012). In addition, bone marrow lesions, defined as ill-defined areas of hyperintense signal intensity on T2- or intermediate-weighted fat-suppressed and short-tau inversion recovery magnetic resonance images, have also been reported in CRPS (Crozier et al. 2003, Varenna et al. 2013) and are thought to overlap with regions of high bone turnover.

Dual-energy X-ray absorptiometry and MRI are established, noninvasive imaging methods that have been used extensively in trials investigating bisphosphonates for treatment of osteoporosis, osteoarthritis, and other conditions.

**Medical resources utilization and health economics data collection**

The WPAI questionnaire is a well validated instrument to measure impairments in work and activities. It has been validated to quantify work impairments for numerous diseases such as asthma,

psoriasis, irritable bowel syndrome, ankylosing spondylitis, and Crohn's disease. In addition, the WPAI questionnaire has been used to compare work impairments between treatment groups in clinical trials or between subjects with different disease severity levels.

## **12.8 Compliance**

Compliance is the adherence to all requirements of the trial protocol.

Trial site compliance will be assured by the implementation of a quality system and the performance of a combination of trial site visits, training, and monitoring visits. Non-compliance should lead to prompt action by the sponsor to secure compliance.

Compliance of the subjects to record their pain intensity assessments will be ensured by capturing the information in an electronic patient reported outcome system at the sites.

Relevant deviations from the protocol will be documented and described in the integrated clinical trial report.

## **13 DOCUMENTATION OF TRIAL DATA**

The trial documentation must be adequate for the reconstruction of the trial.

### **13.1 Case report forms**

Case report forms for each subject will be provided to the investigator by the sponsor in electronic format to document the trial data.

The investigator and personnel delegated the task will use CRFs to record information required by the protocol.

All CRF entries, corrections, and alterations will be made by the investigator or other authorized personnel under their supervision. Entries will be checked against appropriate source documents by authorized sponsor representatives as deemed appropriate in the monitoring guidelines.

The data collection will be done using a validated electronic CRF system. The collected data will reside on servers of the CRF provider. Entry, corrections and alterations of data within the system can only be performed by the investigator or other authorized personnel under their supervision and will be captured by the system's audit trail.

Dedicated users (e.g., the investigator, designated persons at the trial site, authorized sponsor representatives, and from other parties involved, e.g., data management) will be trained and receive access rights according to their role in the trial. All users will have access to the system and be able to review their data on an ongoing basis.

After completion of subjects CRF, the CRF must be signed electronically by the investigator. With the investigator's signature it is confirmed that the data in the CRF are checked, complete, accurate, and in alignment with the source data. Changes to the CRF after initial signing by the investigator need re-signing.

With database lock, the edit rights to the CRFs will be removed but the investigator will retain access to view the CRFs until receipt of a certified copy of all data captured for his or her subjects (site archive). This data will be delivered in a human readable form for retention in his or her files.

### **13.1.1 Subject tetracycline dosing diary**

A subject tetracycline dosing diary will be used to record the intake of tetracycline in US subjects undergoing a transiliac bone biopsy. These data will be supplied to the histomorphometry laboratory for incorporation into the bone biopsy record.

### **13.2 Subject reported outcomes**

Subject reported outcomes will be collected using a validated electronic patient reported outcome system including audit trail.

The investigator will be trained on the use of the electronic patient reported outcome system and the related oversight system. The oversight system will allow the investigator to review all data entered by the respective site subjects on an ongoing basis.

The electronic patient reported outcome will be kept at the trial site and subjects will be instructed on how to use it.

No queries will be issued to the investigator for these data, except for clarification of subject identifiers and any operational issues. No queries will be raised to the subject.

With database lock, the writing access to the electronic patient reported outcome system will be removed. The investigator will receive all data captured for his or her subjects, in a human readable form, on read-only media for his or her files. The information will be provided to the investigator prior to system decommissioning.

### **13.3 External data**

Trial data not recorded in the CRF or subject reported outcome, but requested per protocol (e.g., safety laboratory data, ECG data, bone biopsy data, bone imaging data) will be collected and validated via sponsor internal or external data providers. The data integration into the clinical data and respective quality control measures are described in the Data Management Plan.

### **13.4 Data management**

Data management will be performed by sponsor personnel or by authorized sponsor representatives. Documentation of the responsibilities and delegation thereof will be maintained in the trial master file.

All aspects of the data management process, including data validation and query management, medical coding, handling of external data, data lock procedures are described in the Data Management Plan. Details on data validation are described in the Data Validation Plan.

### **13.5 Source data**

Source data is defined by GCP as “all information in original records and certified copies of original records of clinical findings, observations, or other activities in a clinical trial necessary for the

---

reconstruction and evaluation of the trial. Source data are contained in source documents (original records or certified copies)”).

Source data comprise clinical documentation, data, and records (e.g., clinic/hospital records, clinical and office charts, laboratory notes, memoranda, subjects’ diaries or evaluation checklists, pharmacy dispensing records, recorded data from automated instruments, and data and records arising from departments such as the pharmacy, laboratory, and medico-technical departments) that describe or record the methods, conduct, or results of the trial, the factors affecting the trial, and the actions taken.

All source data arising from the trial will be kept by the investigator, who must provide direct access for trial-related monitoring, audits, ethics committee review, and regulatory inspection.

In certain circumstances, data may only be recorded in the trial-specific CRF and not in other documents. When this occurs, the CRF is considered to be the source document. Data expected to be only recorded in the CRF are race/ethnicity and sex.

The nature and location of all source data/clinical documentation will be identified and documented by the investigator to ensure that all sources of original data required to complete the CRF are known to the sponsor and/or trial site personnel and are accessible for verification during trial-related monitoring, audits, relevant IEC/IRB review, and inspections.

For subject reported outcomes captured directly via the electronic patient reported outcome system, source data is defined as the data residing in the vendor’s database.

### **13.6 Investigator’s site file and the trial master file**

The principal investigator is responsible for the filing of all essential documents in an investigator’s site file. The sponsor is responsible for the timely filing of all essential documents in the trial master file. As applicable, these files must be available at monitoring visits and during audits or regulatory inspections.

After trial completion, the principal investigator must ensure that all source data/documentation related to the trial is recorded, handled, and stored in a way that allows its accurate reporting, interpretation and verification. The principal investigator must take measures to prevent accidental or premature destruction of these documents.

The principal investigator must keep the investigator’s site file, the source data/documentation arising from the trial according to the prescribed record retention period in the country and/or according to the hospital policy, but at least until informed by the sponsor that the trial-related records are no longer required.

## 14 QUANTITATIVE ANALYSES

### 14.1 Statistical methods and sample size determination

#### 14.1.1 Sample size rationale

The sample size rationale for the trial is provided in Section [1.5.1](#).

##### **Subset of subjects for bone biopsies**

The sample size is not based on statistical considerations; bone biopsy specimen evaluation will identify qualitative bone abnormalities such as osteomalacia as well as quantitative indicators of impaired mineralization.

##### **Subset of subjects for bone densitometry and magnetic resonance imaging**

The sample size is not selected based on statistical considerations. Results from this subset of subjects are considered to be sufficient to demonstrate feasibility and explore outcomes of these assessments in trials of neridronic acid in CRPS.

#### 14.1.2 General description of statistical analyses

The statistical analysis of this trial will be performed as described and summarized in the protocol. Full details of the planned statistical analyses will be described in the trial statistical analysis plan.

The statistical analysis of this trial will be planned, performed, and reported by sponsor personnel or by authorized sponsor delegates.

As this is a single-arm trial, no treatment comparisons will be conducted, but development from baseline over time will be investigated. All analyses in this trial will be of exploratory nature. No statistical testing of inference is planned in this trial. There will be no multiplicity adjustment for any of the analyses. All confidence intervals used to describe the data will be determined using a 95% confidence level.

Collected and derived data will be listed.

Summary statistics and graphical methods will be used to describe parameters/variables.

The following descriptive statistics will be produced on the basis of the nature of the relevant variable:

- For continuous variables: number of non-missing observations, arithmetic mean, standard deviations, minimum, first quartile, median, third quartile, and maximum.
- For categorical variables: absolute and relative frequencies and percentages.

#### 14.1.3 Analysis populations (analysis sets)

The analysis populations are defined in Section [1.5.2](#).

#### 14.1.4 Subject disposition

Subject disposition will be summarized descriptively for all enrolled subjects. Discontinuations will be summarized descriptively for all allocated subjects.

### **14.1.5 Analysis of demographic data and other baseline characteristics**

Demographic data, baseline characteristics, medical history, concomitant medications, and exposure will be summarized descriptively for the Safety Set.

### **14.1.6 Analysis of safety data**

#### **14.1.6.1 Adverse events**

A definition of adverse event is given in Section [12.3.1](#).

The original terms recorded in the CRF to identify adverse events will be coded using the most recent version of the Medical Dictionary for Regulatory Activities (MedDRA) at the time of database lock.

All adverse events occurring in a subject administered a trial treatment and which do not necessarily have a causal relationship with this treatment will be defined as TEAEs. In addition, pre-treatment adverse events which worsen during the treatment period are also considered TEAEs.

Treatment emergent adverse events will be summarized for each treatment group by System Organ Class and Preferred Term. Additional summaries by time to onset, duration, intensity, relationship to the IMP, outcome, expectedness, and countermeasures will also be created. To account for the differences in the planned trial duration of the subjects in this trial, an analysis of exposure-adjusted incidence rates will be done in addition to the analysis of crude incidence rates.

Subjects with SAEs will be summarized and additionally listed. Special attention will be given to those subjects who discontinue treatment due to an adverse event or who experience a severe or SAE.

The incidences and incidence rates of all adverse events will be summarized descriptively.

Permanent discontinuations from treatment due to adverse events will be summarized descriptively.

The distribution of time to onset of any TEAE will be summarized using time-to-event methods. A graphical display using Kaplan-Meier methods displaying subjects at risk per time point will also be produced.

#### **14.1.6.1.1 Analysis of the primary endpoint**

The primary endpoint of this trial is a binary endpoint assessing whether or not a subject experienced any TEAE.

#### **14.1.6.2 Safety laboratory values, vital signs, 12-lead ECG**

Safety laboratory values, vital signs, and 12-lead ECG will be summarized descriptively.

Baseline will be the value collected on Day 1 (Visit 2) prior to first administration of IMP.

Sponsor-defined alert ranges will be defined for selected parameters. Subjects with values outside of sponsor-defined alert ranges will be summarized. Subjects with abnormal values will be tabulated and listed separately.

**14.1.6.3 Bone biopsy assessments**

The occurrence of histomorphometric evidence of osteomalacia, defined as osteoid thickness >12.5 µm (corrected for obliquity) and mineralization lag time >100 days (Dempster et al. 2013) will be derived for each assessed subject. All bone biopsy parameters will be descriptively summarized for the Bone Biopsy Set.

**14.1.7 Analysis of efficacy data**

The analysis of all efficacy endpoints will be exploratory and will be summarized using descriptive statistics unless stated otherwise. Analyses will be performed on all post baseline measurements.

**Handling of missing data**

Missing data will not be imputed in this trial. The number of missing data will be included in all descriptive summaries.

An MMRM will be conducted on the observed values of the change in current pain intensity score. An MMRM leads to unbiased estimates if the missingness mechanism is missing-at-random. Due to the long-acting effect of neridronic acid, missing-at-random is considered a clinically plausible assumption. The MMRM in this trial will include the covariate baseline pain intensity and the factors pooled site and visit as fixed effects, and subject as random effect. An unstructured covariance matrix will be used to model the covariance structure. Least squares means, standard errors, and 95% confidence intervals for the change from baseline will be obtained.

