### 1.1.1 Flow diagram summary of the trial

### 1.1.2 Brief description of the sequence and duration of all trial periods

There will be an enrollment period lasting up to 60 days, a treatment period consisting of 4 infusions over 10 days, and a follow-up period of approximately 50 weeks (Visit 6 [Week 2] through Visit 11 [Week 52]). The subjects are expected to be in the trial for approximately 60 weeks (14 months). See Section 1.1.1 for a summary of the trial as a flow diagram and Section 1.6 for a tabular schedule of events.

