**Handling of missing data**

Missing data will not be imputed in this trial. The number of missing data will be included in all descriptive summaries.

A mixed-effects model for repeated measurements (MMRM) will be conducted on the observed values of the change in current pain intensity score. An MMRM leads to unbiased estimates if the missingness mechanism is missing-at-random. Due to the long-acting effect of neridronic acid, missing-at-random is considered a clinically plausible assumption. The MMRM in this trial will include pooled site, baseline pain intensity and week as fixed effects and subject as a random effect. An unstructured covariance matrix will be used to model the covariance structure. Least squares means, standard errors, and 95% confidence intervals for the change from baseline will be obtained.

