#### **11.1.2 Treatment period**

The target dosing schedule is Day 1, Day 4, Day 7, and Day 10. Flexibility of  $\pm 1$  day is allowed for Day 4, Day 7, and Day 10, keeping the overall duration of the infusions within the 10-day period (11 days if Day 10 +1 day). A minimum period of 48 hours is required between infusions.

Central safety laboratory data from the previous visit, in particular eGFR, must be evaluated prior to each infusion.

See Section 9.3.2 for details of temporary suspension of IMP.

Due to the number of procedures and assessments at the infusion visits, subjects should arrive at the site at least 1 hour to 2 hours prior to the start of the infusion; subjects will remain at the center for 1 hour after the end of the infusion for evaluation.

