#### 13.2.1.1 Current pain intensity

Current pain intensities and the corresponding changes from baseline will be presented in a subject data listing. Baseline current pain intensities will be flagged in the listing. Current pain intensities including their changes from baseline will be descriptively summarized by visit.

The change from baseline values at all post-baseline visits from Visit 3 through Visit 11 will be analyzed using a mixed model for repeated measures (MMRM), including the covariate baseline pain intensity, and the factors pooled site and visit as fixed effects, and subject as random effect. An unstructured covariance matrix will be used to model the covariance structure. The degrees of freedom of the denominator will be estimated using the Kenward-Roger approximation ([Kenward and Roger 1997](#)).

If the default Newton-Raphson algorithm used by statistical analysis software (SAS) PROC MIXED fails to converge, the Fisher scoring algorithm up to iteration 2 will be used (via the SCORING=2 option of the PROC MIXED statement) to obtain the initial values of covariance parameters ([Mallinckrodt et al. 2008](#)). If this alternative also fails to converge, then in addition the no-diagonal factor analytic structure (via the TYPE=FA0(T) option of the REPEATED statement, where T=9 is the total number of post-baseline visits, visits 3 to 11) will be used, which effectively performs the Cholesky decomposition of the covariance matrix and is numerically more stable. The first algorithm that leads to convergence in this sequence of fallback measures will be the algorithm used for the primary analysis of the trial.

Point estimates (LSmeans), standard errors, and 95% CIs for the factor visit in the MMRM model representing the change from baseline at each visit will be presented. A graphical plot of the model-based estimates and the 95% CI of the change from baseline of current pain intensity scores will be created.

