### **13.3.1 Average and worst pain intensity**

Worst and average pain intensities will be added to the subject data listing of current pain values (see Section 13.2.1.1). The listing will be presented by pain type (average, current, and worst).

Worst and average pain intensities will be added to the descriptive summary of current pain. The summary will be presented by pain type.

Change in the worst pain intensity and average pain intensity for all post-baseline visits will be analyzed using the same statistical model as the one used for the current pain.

Point estimates least square means (LSmeans), standard errors, and 95% CIs for the factor visit in the MMRM model representing the change from baseline at each visit will be presented. Results will be added to the model-based summary of current pain.

Graphical plots of the model-based estimates and the 95% CI of the change from baseline of worst and average pain intensity will be created. The plots will be added to the graphical plots of current pain intensity scores.

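### The pain MMRM fits one baseline slope to all nine visits, so later-visit means can be biased under missing-at-random dropout if the true slope changes over time; adding baseline-by-visit is a cheap, minor improvement

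*Protocol*

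**What the plan says.** The pain model is described in three places, with the same terms each time.

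- Protocol 14.1.7 (Handling of missing data): "The MMRM in this trial will include the covariate baseline pain intensity and the factors pooled site and visit as fixed effects", with subject as a random effect and an unstructured covariance.
- Protocol 1.5.3: "The MMRM in this trial will include pooled site, baseline pain intensity and week as fixed effects and subject as a random effect".
- SAP 13.2.1.1: "including the covariate baseline pain intensity, and the factors pooled site and visit as fixed effects, and subject as random effect".

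SAP 13.2.1.1 fixes the number of visits in the model: "where T=9 is the total number of post-baseline visits, visits 3 to 11". Visit 3 is the Day 4 infusion visit (Protocol 11.1.2: "The target dosing schedule is Day 1, Day 4, Day 7, and Day 10") and Visit 11 is Week 52. The visit LSmeans, standard errors and 95% intervals are reported and plotted for every visit. Under SAP 13.3.1, worst and average pain "will be analyzed using the same statistical model as the one used for the current pain". SAP 13.2 asks for the secondary efficacy endpoints overall and in the two CRPS-duration subgroups.

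Both protocol sections justify the model with one sentence: "An MMRM leads to unbiased estimates if the missingness mechanism is missing-at-random". Neither document states the baseline value at which the LSmeans are evaluated. SAP 13.2.2 lists no sensitivity analysis.

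**The concern.** Missing-at-random is not enough by itself to make a likelihood-based repeated-measures model unbiased. The mean model must also be right. Here the covariance among post-baseline visits is left free, but the relation of change to baseline pain is held constant over a year.

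The slope of change on baseline at visit t is cov(Y_t, B)/var(B) − 1, where Y_t is pain at visit t and B is baseline pain. A common slope requires the covariance with baseline to be the same at Day 4 as at Week 52. There are reasons to doubt this. At Day 4 only one of the four infusions has been given. Responders are defined by percentage decrease, and if effects are roughly proportional to baseline, the slope steepens as the effect grows. Baseline is a single rating of current pain, whose association with later ratings may well weaken over time. These are reasons for doubt, not data.

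At stake are the model-based changes in current pain at Weeks 12 and 26, which are secondary endpoint time points, and the Week 52 value shown beside them.

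**Working it through.** **No figure to reproduce.** The documents state no bias, power or derived sample size for this model. The visit count agrees: Visits 3 to 11 are 9 visits.

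**Mechanism.** Let b̄ be the mean baseline of all treated subjects, b̄_R that of subjects still observed at visit t, β_t the true slope at t, and β̂ the fitted common slope. Ignoring the help from earlier visits,

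bias at t ≈ (β̂ − β_t)(b̄ − b̄_R).

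It is zero if β̂ = β_t, or if dropout is unrelated to baseline so that b̄ = b̄_R.

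**Inputs from the documents.** About 290 subjects; baseline NRS at least 4; 9 visits; unstructured covariance; 95% intervals.

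**Assumed inputs.** Baseline spread over 4 to 10. Residual SD rising from 1.3 to 2.4. Correlation either autoregressive (0.85) or exchangeable (0.6). True slopes either −0.4 at every visit, or running from Day 4 to Week 52 as 0 to −0.3, −0.1 to −0.5, or 0 to −0.7. Monotone dropout from Visit 7, reaching 20% or 35% by Week 52, with log-odds 0, 0.25 or 0.5 per baseline point. Pooled site was left out. Fits were by maximum likelihood.

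**Large-sample bias of the planned model (60,000 subjects per scenario, NRS points).**

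| Condition | Week 12 | Week 26 | Week 52 |
|---|---|---|---|
| Equal slopes | 0.01 or less | 0.01 or less | 0.01 or less |
| Dropout unrelated to baseline | about 0.01 or less | about 0.01 or less | about 0.01 or less |
| Unequal slopes and baseline-dependent dropout | 0.004 to 0.05 | 0.006 to 0.085 | 0.015 to 0.17 |
| Same, with baseline-by-visit added | 0.01 or less | 0.01 or less | 0.01 or less |

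**One case through the formula.** Slopes 0 to −0.7, exchangeable, 35% dropout, log-odds 0.5, Week 52. The plain observed mean is biased by 0.343, so b̄ − b̄_R ≈ 0.343/0.7 = 0.49. The fitted common slope is 0.049, so the formula gives (0.049 + 0.7) × 0.49 ≈ 0.37. The model's actual bias is 0.174. The unstructured covariance thus recovers about half through the earlier visits.

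**Trials of 290 subjects (400 runs each; 35% dropout, log-odds 0.5).** Bias is against the mean change of the whole treated sample; the Monte Carlo SE of coverage is about 1.1 percentage points.

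| True slopes, correlation | Model | Bias at Weeks 12 / 26 / 52 | 95% CI coverage (%) |
|---|---|---|---|
| −0.4 throughout, AR | planned | 0.002 / −0.005 / −0.013 | 94.2 / 94.2 / 94.2 |
| −0.4 throughout, exch. | planned | −0.005 / 0.001 / −0.010 | 92.0 / 95.0 / 94.5 |
| −0.1 to −0.5, AR | planned | 0.020 / 0.031 / 0.079 | 94.5 / 93.8 / 91.5 |
| −0.1 to −0.5, exch. | planned | 0.026 / 0.054 / 0.099 | 92.8 / 94.0 / 91.5 |
| 0 to −0.7, AR | planned | 0.031 / 0.054 / 0.136 | 93.2 / 93.5 / 87.8 |
| 0 to −0.7, exch. | planned | 0.044 / 0.085 / 0.158 | 93.2 / 92.0 / 85.0 |
| all three, AR | with interaction | 0.001 / −0.005 / −0.014 | 94.2 / 95.5 / 95.2 |
| all three, exch. | with interaction | −0.005 / 0.002 / −0.010 | 92.0 / 95.5 / 95.2 |

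With unequal slopes, the planned model's bias in SE units is 0.16 to 0.34 at Week 12, 0.23 to 0.59 at Week 26 (0.031/0.135 to 0.085/0.144) and 0.48 to 0.91 at Week 52 (0.079/0.164 to 0.158/0.173).

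**Direction.** In these runs subjects with higher baseline leave more often, and improvement is understated. A separate set of simulations (slopes −0.15 to −0.58; 17–19% missing at Week 26 and 27–29% at Week 52) gave absolute bias of 0.025 to 0.051 at Week 26 and 0.044 to 0.086 at Week 52, with either sign depending on who leaves.

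**Reference baseline.** If baseline is averaged over records rather than subjects, early leavers count less. In the case worked above the reference value falls by 0.143. With slopes equally spaced over the nine visits, the Week 26 slope is −0.525, so the interaction model's Week 26 mean moves by −0.143 × −0.525 ≈ 0.075. The simulated values agree: 0.073 at the record mean against −0.003 at the subject mean. The interaction alone does not remove this shift.

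**The case against.** The strongest reply is that the effect is hypothetical and small. It needs two conditions together, and the documents give no slope, correlation, SD or dropout rate for this trial. Even in the stronger scenarios, bias at the endpoint weeks stays below 0.1 point and coverage there is 92% to 94.5%. The SAP's absolute responder threshold is 2 points. The trial is a single-arm safety study, all analyses are exploratory, nothing is tested, and Protocol 8.1 already calls for caution with the efficacy results. Dropout driven by observed post-baseline pain is also missing at random; the unstructured covariance is designed for it, and these runs did not examine it. The plan also limits loss: subjects who stop IMP are kept in follow-up (Protocol 9.3.1 and 9.3.2), and early-termination data are assigned to scheduled visits (SAP 20.1.1.14).

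All of that stands, and it sets the severity. It does not supply the missing condition in the unbiasedness sentence or give a reason for the equal-slope restriction.

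A reader might also infer that the MMRM is the plan's only protection against dropout. The documents do not support that. SAP 13.2.1.2 and 13.2.1.3 count missing pain and PGIC scores as non-response. For the continuous pain change, though, no imputation and no sensitivity analysis stand beside the MMRM, which in these scenarios is less biased than plain observed means.

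**Conclusion.** The point holds in conditional form and is minor. The planned visit means can be biased under missing-at-random dropout if the baseline slope changes over time and dropout depends on baseline pain. Under the assumed values the size is 0.004 to 0.085 NRS point at Weeks 12 and 26, and up to about 0.17 at Week 52. Loss of coverage is noticeable mainly at Week 52 (85% to 91.5% in the stronger scenarios).

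A reader might infer that the later means are in fact biased, or that the protocol's sentence is simply false. Neither follows. With equal slopes the bias vanishes even under strongly baseline-dependent dropout, and the documents contain nothing that shows the slopes differ. The sentence is incomplete because it leaves out that the mean model must be correct. All magnitudes are illustrative, because every slope, SD, correlation and dropout rate behind them is assumed.

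**What to change.** - In SAP 13.2.1.1, and through it 13.3.1, add baseline pain by visit as a fixed effect. Align Protocol 1.5.3 and 14.1.7, or record the change in SAP 7.1. Leave the rest of the model unchanged.
- State that visit LSmeans are evaluated at the mean baseline over all FAS subjects in the analysis, one value per subject and not averaged over records. Apply the same rule to the TCS and to each duration subgroup, using that analysis's own subjects.
- Qualify the unbiasedness sentence: it needs missing-at-random and a correctly specified mean model.

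The cost is 9 − 1 = 8 more fixed-effect parameters, with about 290 subjects and nine visits, and no new data. If slopes are equal, little precision is lost: the Week 52 SE rose from 0.160 to 0.164 and from 0.157 to 0.161 in the two equal-slope settings. The extra terms are somewhat more demanding in the duration subgroups, whose sizes the documents do not give.
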